1 INTRODUCTION

1.1 Background

Hen egg allergy is a common and serious condition that disproportionately affects children and is associated with severe hypersensitivity reactions, including life-threatening anaphylaxis. The prevalence of egg allergy is estimated to be approximately 0.5% to 2.5% in Western countries (Loh, 2018). While egg allergy is typically outgrown, longitudinal studies have shown this may not occur until the second decade of life, with egg allergy persisting in approximately 20% of individuals aged 18 years (Clark, 2011; Savage, 2007). Higher peak egg-specific immunoglobulin E (IgE) levels, higher initial egg-specific IgE, and initial allergic reaction characteristics have been suggested to be predictive of persistence of egg allergy into adulthood (Sicherer, 2014; Lemon-Mule, 2008; Savage, 2007).

Two main egg allergy phenotypes are recognized in the clinic, allergy to both raw egg and baked egg, and allergy to raw egg only (Bartnikas, 2013; Tan, 2013; Turner, 2013; Lieberman, 2012; Osborne, 2011; Lemon-Mule, 2008). Approximately 20% to 30% of individuals with egg allergy are allergic to both raw egg and baked egg, and 70% to 80% of individuals with egg allergy are allergic to raw egg only (Tan, 2013; Turner, 2013; Lieberman, 2012; Osborne, 2011; Lemon-Mule, 2008). Allergy to well-cooked egg (baked egg) has been shown to resolve at a more rapid rate than allergy to uncooked egg (raw egg) (Clark, 2011).

The current standard of care for the management of egg allergy is dietary avoidance of egg and education of the patient/family on recognition and management of allergy symptoms and appropriate use of rescue medications (eg, epinephrine auto-injectors). Regular consumption of baked egg by patients with hen egg allergy who tolerate baked egg has been proposed to accelerate the development of tolerance to raw egg compared with avoidance (Leonard, 2012). However, it is not known whether the decreased time to resolution of hen egg allergy is due to regular consumption of baked egg by patients allergic to raw egg only or if these patients represent an egg allergy phenotype with a greater probability of outgrowing the egg allergy (Lambert, 2017; Dang, 2014).

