1.6 Rationale for Study Design

Egg OIT has been widely studied in recent years but the studies varied significantly in study design. Despite the differences between protocols, all studies utilizing nonhydrolyzed egg products showed favorable desensitization responses with egg OIT and an expected safety profile comprised of mainly mild to moderate allergic adverse events ([Romantsik, 2018](#)). These data support the initiation of a phase 2 clinical study for AR201.

Subjects up to 26 years of age will be enrolled due to the high unmet medical need in this population, indicated by the increased risk of fatal food-induced anaphylaxis in adolescents and young adults ([Bock, 2001](#)). Given the natural history of spontaneous resolution, adults aged 26 years or older will not be enrolled in this study. A lower age limit of 4 years was selected based on the known spontaneous resolution rate of egg allergy, which is the greatest in younger children ([Sicherer, 2014](#)).

Randomization will be stratified by baseline tolerance or reactivity to baked whole egg, as baked egg tolerance is a known predictor for spontaneous resolution of egg allergy ([Leonard, 2015](#)).

A standardized method for OIT with AR201 will be used that consists of initial dose escalation at low doses, gradual up-dosing over time to limit allergic reactions (single dose escalation every 2 weeks), and maintenance dosing at 300 mg/day dried egg white protein. The aim of treatment with AR201 is to induce and maintain a state of desensitization to egg that is sufficient to protect a patient with egg allergy from severe symptoms in case of accidental exposure despite maintaining an egg-avoidant diet. Therefore, the maintenance dose is lower than that used in clinical studies whose aim was to achieve nutritional inclusion of egg in the diet. The AR201 dosing regimen is based in part on that used by Buchanan et al, where 24 months of maintenance treatment with 300 mg egg OIT resulted in 6 of 7 subjects (85.7%) tolerating > 2 g egg white powder in an exit oral food challenge, an amount that is 6-fold greater than the maintenance dose ([Buchanan, 2007](#)).

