10 STATISTICAL METHODS

10.1 Statistical and Analytical Plans

The statistical methods and data presentations for reporting the study will be described in detail in the statistical analysis plan.

Randomization will be central and treatment allocation will be 2:1 (AR201 or placebo). Randomization will be stratified by baseline reactivity (tolerant or intolerant) to baked egg in an open baked whole egg food challenge at screening. Subjects who tolerate approximately 2000 mg cumulative baked egg protein without dose-limiting allergy symptoms will be considered baked egg tolerant. Subjects who do not complete the screening open baked whole egg food challenge for reasons other than dose-limiting symptoms and who have a clear clinical history of tolerance to baked egg may be considered baked egg tolerant after discussion with the medical monitor. All other subjects will be considered baked egg intolerant.

Data for demographic and baseline characteristics, efficacy, and safety will be summarized by treatment group (AR201 or placebo). Summary statistics will include the mean, number

of observations, standard deviation, median, minimum and maximum values for continuous variables, and frequencies and percentages for categorical variables.

Statistical significance is defined as $p < 0.05$ and tests will be 2-sided, unless otherwise specified. CIs will be calculated at the 95% level, reflecting a 2-sided type I error of 0.05.

The statistical methods and statistical analysis plan may be affected by a pandemic, epidemic, or other emergency not related to the study as described in [Appendix 3](#).

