10.3 Determination of Sample Size

A sample size of 84 subjects randomly assigned at a ratio of 2:1 to AR201 or placebo (56 AR201, 28 placebo) provides 89% power to demonstrate a significant treatment difference of at least 35% in desensitization response rate with AR201 compared with placebo for the primary efficacy endpoint of the proportion of subjects tolerating an at least 1000 mg single dose of dried egg white protein with no more than mild allergy symptoms during the exit DBPCFC. The sample size calculations are based on a 2-sided alpha of 0.05, and 2-sample comparison of binomial proportions with an assumed maximum desensitization rate of 60% in the AR201 group and 25% in the placebo group. Treated subjects who discontinue early from the study will be considered nonresponders.

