10.5 Analysis of Efficacy

10.5.1 Primary Efficacy Analyses

The primary objective assesses the efficacy of AR201 treatment in subjects aged 4 to 26 years, inclusive, with hen egg allergy.

The primary efficacy endpoint is the proportion of subjects treated with AR201 compared with placebo who tolerate a single highest dose of at least 1000 mg dried egg white protein with no more than mild allergy symptoms at the exit DBPCFC.

The ITT population and the Cochran-Mantel-Haenszel test will be used for these analyses. Subjects tolerating an at least 1000 mg single challenge dose of dried egg white protein will be considered responders; subjects who do not tolerate an at least 1000 mg single challenge dose of dried egg white protein will be considered nonresponders. Nonresponders will also include subjects who withdraw consent or discontinue early anytime before the exit DBPCFC.

Desensitization response rates and associated 95% CIs for each stratum will be presented for each treatment group using Wald CIs. The 95% CI for the treatment difference (desensitization rate for AR201 treatment minus desensitization rate for placebo) will be constructed by combining the stratum-specific differences using the Cochran-Mantel-Haenszel weights.

Full details will be provided in the statistical analysis plan.

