10.5.2 Secondary Efficacy Analyses

Secondary efficacy endpoints will be assessed as follows:

The proportion of subjects who tolerate a single highest dose of at least 300 mg dried egg white protein with no more than mild symptoms during the exit DBPCFC will be assessed using the methods described for the primary endpoint ([Section 10.5.1](#)).

The proportion of subjects who tolerate a single highest dose of at least 600 mg dried egg white protein with no more than mild symptoms during the exit DBPCFC will be assessed using the methods described for the primary endpoint ([Section 10.5.1](#)).

The maximum severity of allergy symptoms after consuming dried egg white protein during the exit DBPCFC will be assessed by tabulating the number and percentage of subjects by maximum severity of allergy symptoms at the exit DBPCFC and by treatment group. The Cochran-Mantel-Haenszel test stratified by baseline reactivity to baked egg in an open baked whole egg food challenge at screening will be used to test for a treatment difference.

Full details will be provided in the statistical analysis plan.

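### Section 10.5.1 prescribes Wald 95% intervals for stratum-by-arm response rates; in the smallest cell, inferred at 6 to 8 placebo subjects, they would cover about 78–87% if the rate there is the assumed 25%

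*Protocol*

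**What the plan says.** Section 10.5.1 tests the primary endpoint (tolerating at least 1000 mg at the exit food challenge) with a Cochran-Mantel-Haenszel test in the ITT population. For the accompanying display it says: "Desensitization response rates and associated 95% CIs for each stratum will be presented for each treatment group using Wald CIs". The strata are baked-egg tolerant and intolerant, the only stratification factor. Section 10.5.2 extends the approach to the 300 mg and 600 mg secondary endpoints, each of which "will be assessed using the methods described for the primary endpoint".

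Section 10.1 sets the level for all intervals: "CIs will be calculated at the 95% level, reflecting a 2-sided type I error of 0.05".

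Section 10.3 plans 56 AR201 and 28 placebo subjects and works from "an assumed maximum desensitization rate of 60% in the AR201 group and 25% in the placebo group". These are rates for whole arms. The protocol gives no expected split between strata, no stratum-specific rates, and no alternative interval for small cells or for 0% or 100% response. Full details are deferred to the SAP, but the type of interval for the stratum rates is already settled in the protocol.

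**The concern.** The Wald interval uses the observed proportion to estimate its own standard error. In a small sample this breaks down when responders are few: with none, the estimated standard error is zero and the interval has no width; with one or two, the lower limit falls below zero.

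One cell is likely to be very small. Section 1.1 reports: "Approximately 20% to 30% of individuals with egg allergy are allergic to both raw egg and baked egg". Applied to 28 placebo subjects, that leaves a handful in the intolerant stratum. It is also the cell where responders are likely to be fewest, since Section 1.6 notes that "baked egg tolerance is a known predictor for spontaneous resolution of egg allergy".

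At stake is the by-stratum table of the primary endpoint, where readers will look to see whether the effect holds in baked-egg-intolerant subjects. A placebo interval of [0%, 0%], or one with an impossible negative limit, would misstate the uncertainty there and invite a change of method after unblinding.

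**Working it through.** **Inputs**
- Arm sizes 56 and 28; overall rates 60% and 25%; two-sided alpha 0.05 (Section 10.3).
- Nominal interval level 95% (Section 10.1).
- Share allergic to both raw and baked egg, 20–30% (Section 1.1), taken as an assumption for this trial.
- Early discontinuations count as nonresponders (Section 10.3), so dropout does not shrink the cells.

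**The plan's own figure.** Power for 60% versus 25% with 56 and 28 subjects is 88.0% by the pooled normal approximation and 88.5% by exact enumeration of the uncorrected chi-square test. The stated 89% is reproduced to within about a point. It does not depend on the interval method.

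**Cell sizes**
- Placebo intolerant: 28 × 0.20 = 5.6 to 28 × 0.30 = 8.4, so about 6 to 8.
- Placebo tolerant: 28 × 0.70 = 19.6 to 28 × 0.80 = 22.4, so about 20 to 22.
- AR201 intolerant: 56 × 0.20 = 11.2 to 56 × 0.30 = 16.8, so about 11 to 17.
- AR201 tolerant: 56 × 0.70 = 39.2 to 56 × 0.80 = 44.8, so about 39 to 45.

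**Formula.** With x responders among n and p̂ = x/n, the Wald interval is p̂ ± 1.96·√(p̂(1 − p̂)/n). Exact coverage at a true rate p is the sum of the Binomial(n, p) probabilities of every x whose interval contains p.

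**Placebo intolerant cell at p = 25%**
- n = 6: the interval contains 25% only for x = 1, 2, 3. Coverage = 0.3560 + 0.2966 + 0.1318 = 78.4%.
- n = 7: x = 1 to 4. Coverage = 0.3115 + 0.3115 + 0.1730 + 0.0577 = 85.4%.
- n = 8: x = 1 to 4. Coverage = 0.2670 + 0.3115 + 0.2076 + 0.0865 = 87.3%.

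**Degenerate intervals in the same cell**
- x = 0 gives [0%, 0%]. Its probability is 0.75ⁿ: 17.8%, 13.3% and 10.0% for n = 6, 7, 8.
- x = 1 or 2 gives a negative lower limit: 1/7 gives −12% to 40%, and 2/7 gives −5% to 62%.
- Either outcome: 83%, 76% and 68% for n = 6, 7, 8.

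**Comparison of methods, placebo intolerant cell**

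| n | True rate | Wald | Wilson | Clopper-Pearson |
|---|---|---|---|---|
| 6 | 25% | 78.4% | 96.2% | 99.5% |
| 7 | 25% | 85.4% | 92.9% | 98.7% |
| 8 | 25% | 87.3% | 97.3% | 99.6% |
| 6 | 10% | 46.7% | 98.4% | 98.4% |
| 7 | 10% | 51.9% | 97.4% | 99.7% |
| 8 | 10% | 56.5% | 96.2% | 99.5% |

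The 10% rows are a sensitivity value; the protocol gives no rate for this stratum. At 10%, [0%, 0%] occurs in 43–53% of trials. For 0/7 the Wilson interval is 0% to 35%.

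**Sensitivity to cell size.** At 25%, Wald coverage is below 95% for every n from 5 to 28, with a maximum of 94.1% at n = 18. It does not rise steadily: 92.4% at n = 10, 82.7% at n = 12, 88.9% at n = 14 (an even split of the placebo arm). At n = 14 and 10% it is 76%. If the placebo intolerant count is itself Binomial(28, 0.25), average Wald coverage is 81% at a 25% rate and 50% at 10%; Wilson averages 96% at both.

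**Other cells under the 20–30% split.** Wald covers 90–93% in placebo tolerant (25%), 90–94% in AR201 intolerant (60%) and 93–95% in AR201 tolerant (60%).

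**Secondary endpoints.** The lower thresholds may bring higher placebo rates. At an assumed 40–50% and n = 6 to 8, Wald coverage is 78–95%.

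**The case against.** Four points can be made against this.

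*The cell size and the rate are borrowed.* The 20–30% describes egg-allergic people generally, whereas this trial enrols sensitised subjects who react at 300 mg or less. Section 10.1 also makes intolerance the default for anyone not classed as tolerant ("All other subjects will be considered baked egg intolerant"), which can only enlarge that stratum. The 25% is a whole-arm rate, and the rate among intolerant subjects may well be lower. All of this stands, so 78–87% is conditional. It does not rescue the method: a larger cell does not reliably restore coverage, and a lower rate makes it worse.

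*Nothing inferential uses these intervals.* This is correct. No test, alpha or power calculation depends on them, and it is why the point is minor. Any interval from about 7 subjects is also wide: at n = 7 and 25% the mean width is 55 points for Wald and 52 for Wilson.

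*Negative limits are usually shown as zero.* Truncation would tidy the display, so the 68–83% figure should not be read as a rate of misleading results. Truncation leaves coverage unchanged, however, and does nothing for [0%, 0%].

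*The SAP may add a small-cell rule.* It may, but the protocol names Wald without exception, so such a rule would depart from the protocol.

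**Conclusion.** The concern holds, as a minor one. The protocol itself names an interval that does not deliver its own 95% level in the smallest displayed cell: about 78–87% coverage at a 25% rate with 6 to 8 subjects, and 47–57% if the rate there is 10%. At the protocol's rate there is a 10–18% chance of reporting a placebo rate with no uncertainty at all.

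The size rests on two assumptions: that the background 20–30% applies to this trial, and that the whole-arm 25% applies to the intolerant stratum. Under that split the shortfall is large only in this cell; under an even split it would be 89% coverage at 25% and 76% at 10%.

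The primary test and the stated 89% power are untouched. The interval for the combined treatment difference is outside this point, because the protocol does not give its variance formula.

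**What to change.** In Section 10.5.1, name Wilson (score) intervals in place of Wald for the response rates by stratum and treatment group; Clopper-Pearson is an acceptable, more conservative alternative. Because Section 10.5.2 refers back to this method, the 300 mg and 600 mg endpoints follow without further edits. The SAP should carry the same wording.

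The cost is a change of two words and a standard software option; data, sample size and primary test are unchanged. At n = 7 the mean widths for Wald, Wilson and Clopper-Pearson are 55, 52 and 62 points at a 25% rate, and 30, 44 and 51 points at 10%. Wilson therefore widens the interval where Wald is falsely narrow. Wilson is not exactly 95% at every size either (92.9% at n = 7 and 25%), but it never collapses to zero width or goes below zero. If guaranteed coverage of at least 95% is wanted, Clopper-Pearson gives it at the price of wider intervals.

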10.5.2 Secondary Efficacy Analyses

Secondary efficacy endpoints will be assessed as follows:

The proportion of subjects who tolerate a single highest dose of at least 300 mg dried egg white protein with no more than mild symptoms during the exit DBPCFC will be assessed using the methods described for the primary endpoint ([Section 10.5.1](#)).

The proportion of subjects who tolerate a single highest dose of at least 600 mg dried egg white protein with no more than mild symptoms during the exit DBPCFC will be assessed using the methods described for the primary endpoint ([Section 10.5.1](#)).

The maximum severity of allergy symptoms after consuming dried egg white protein during the exit DBPCFC will be assessed by tabulating the number and percentage of subjects by maximum severity of allergy symptoms at the exit DBPCFC and by treatment group. The Cochran-Mantel-Haenszel test stratified by baseline reactivity to baked egg in an open baked whole egg food challenge at screening will be used to test for a treatment difference.

Full details will be provided in the statistical analysis plan.

10.6 Analysis of Safety

All safety analyses will be performed using the safety population. Safety data will be summarized and listed by treatment received.

Safety data will be collected from signed informed consent and assent (where required) through 14 days after the last dose of study product, or through study exit for subjects receiving AR201 treatment in a follow-on study.

Adverse events will be classified by system organ class and coded to preferred term using the Medical Dictionary for Regulatory Activities (MedDRA). Adverse events will be classified by severity using the systemic allergic reaction grading system for systemic allergic reactions including anaphylaxis, and the general adverse events grading system for all other adverse events ([Section 8.6](#)). Anaphylaxis is defined as a severe, potentially life-threatening systemic allergic reaction (ie, grade ≥ 3 per the systemic allergic reaction grading system [[Section 8.6](#)]) that meets the criteria for anaphylaxis per [Section 8.4.1](#).

Summaries of the safety of AR201 and placebo treatment during the study will include the following:

- Overall summary of adverse events
- Incidence of all nonserious and serious adverse events
- Incidence of adverse events by severity grade
- Incidence and severity of treatment-related adverse events
- Incidence of dose modifications
- Exposure-adjusted event rates for the most frequent adverse events (ie, adverse events in $\geq 5\%$ of the safety population)
- Exposure-adjusted event rates for the most frequent treatment-related adverse events (ie, adverse events in $\geq 5\%$ of the safety population)
- Incidence of early treatment discontinuation due to adverse events and due to chronic or recurrent GI adverse events
- Separate summaries will be presented for adverse events considered allergic reactions, systemic allergic reactions, use of epinephrine, and accidental/nonaccidental food allergen exposure

Adverse events with onset before the first dose of study treatment will be listed only.

All medications will be coded using the World Health Organization Drug Dictionary (WHO-DD). Medications will be listed and summarized by Anatomical Therapeutic Chemical (ATC) classification system level 1 and preferred name.

- Prior and concomitant medications, excluding rescue medications, will be summarized separately by ATC class, preferred name, and treatment.

- Rescue medications used during screening, initial dose escalation, up-dosing, maintenance, and overall (including all rescue medications reported on the case report form) will be summarized by ATC class, preferred name, and treatment received.
- All prior, concomitant, and rescue medications will be listed by subject.

Summary statistics will be provided for the ACT, C-ACT, lung function data, EASI, TNSS, and laboratory data if relevant. These data will also be listed by subject.

Full details for the safety analyses will be provided in the statistical analysis plan.

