10.2 Analysis Populations

The intent-to-treat (ITT) population (ie, full analysis set) will be defined as all subjects who receive any part of one dose of study product. The ITT population will be used for all efficacy analyses unless otherwise specified, and analyzed according to randomized treatment. If no subjects receive the incorrect treatment, the ITT population will be the same as the safety population.

The completer population will be defined as all subjects in the ITT population who complete study treatment and have an evaluable exit DBPCFC (completion of at least the dried egg white food challenge day).

The per protocol population may be defined if it is sufficiently different from the completer population. The per protocol population will include all subjects in the completer population who have no major protocol deviations.

The safety population will be defined as all subjects who receive any randomized study treatment (ie, who receive any part of one dose of study product and complete one study visit). The safety population will be used for all safety analyses and analyzed according to treatment received.

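### Selecting events for the exposure-adjusted tables at 5% of both arms pooled acts, under 2:1 allocation, as a cut-off of about 7.5% to 9.3% for an event seen only on AR201

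*Protocol*

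**What the plan says.** The list of safety summaries in Protocol Section 10.6 contains two exposure-adjusted tables. The first is "Exposure-adjusted event rates for the most frequent adverse events", defined in brackets as events in at least 5% of the safety population; the second is "Exposure-adjusted event rates for the most frequent treatment-related adverse events", with the same bracketed definition. The denominator is given in Section 10.2: "The safety population will be defined as all subjects who receive any randomized study treatment". That is both arms together, and neither bullet adds a per-arm alternative.

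Section 10.6 also says that safety data are presented by treatment received. This governs how a selected event is displayed, not which events are selected. The remaining summaries in the list (overall, all nonserious and serious events, severity grade, treatment-related events, discontinuations, allergic and systemic allergic reactions, epinephrine use, food allergen exposure) carry no frequency cut-off. The section leaves full details to the statistical analysis plan, which is not at hand, but it states this selection rule and its denominator itself, twice.

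**The concern.** With unequal allocation, a percentage of the pooled population is not the same percentage of each arm. An event confined to AR201 is diluted by the placebo subjects in the denominator, so a nominal 5% becomes a higher bar on AR201 and a higher one still for an event confined to placebo.

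The two tables affected are the only ones listed in Section 10.6 that account for time on treatment. Time on treatment could differ between arms, because the discontinuation rules in Sections 5.3 and 8.7.3.2 are largely driven by dose-related symptoms. What is at stake is whether low-frequency AR201-only events receive an exposure-adjusted rate in a first-in-human study (Section 1.2) with safety and tolerability as a secondary objective (Section 2.2). No efficacy result is involved.

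**Working it through.** **Inputs.** The threshold is 5% of the safety population (Section 10.6), which is all treated subjects (Section 10.2). For size and allocation, Section 10.3 states: "A sample size of 84 subjects randomly assigned at a ratio of 2:1 to AR201 or placebo (56 AR201, 28 placebo) provides 89% power".

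**The plan's own figure.** The protocol states no effective per-arm cut-off. The stated power was checked to confirm that the arm sizes are the ones used. With 60% against 25%, the pooled proportion is (0.25 × 28 + 0.60 × 56)/84 = 0.483. The null standard error is √(0.483 × 0.517 × (1/28 + 1/56)) = 0.1157, and the alternative one is √(0.25 × 0.75/28 + 0.60 × 0.40/56) = 0.1048. Power is Φ((0.35 − 1.96 × 0.1157)/0.1048) = 88.0%. The exact power of the uncorrected chi-square test is 88.5%. Both agree with 89% to within about a point, so 56 and 28 are taken as given.

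**Cut-off at 84 treated.**
- Minimum count: 5% × 84 = 4.2, so 5 subjects.
- Seen only on AR201: 5/56 = 8.9%. Before rounding to whole subjects it is 5% × 84/56 = 7.5%.
- Seen only on placebo: 5/28 = 17.9%.
- AR201-only in 3 subjects: 3/56 = 5.4% of the arm but 3/84 = 3.6% pooled, so left out.
- AR201-only in 4 subjects: 4/56 = 7.1% of the arm but 4/84 = 4.8% pooled, so left out.
- Split 3 on AR201 and 2 on placebo: 5/84 = 6.0% pooled, so shown.

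**Other numbers treated.** The Synopsis gives 84 only as an approximate number, so the calculation is repeated, assuming 2:1 throughout.

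| Treated (AR201) | Minimum count | AR201-only cut-off | AR201-only counts at or above 5% of the arm but left out |
|---|---|---|---|
| 72 (48) | 4 | 8.3% | 3 |
| 75 (50) | 4 | 8.0% | 3 |
| 80 (53) | 4 | 7.5% | 3 |
| 81 (54) | 5 | 9.3% | 3 and 4 |
| 84 (56) | 5 | 8.9% | 3 and 4 |
| 90 (60) | 5 | 8.3% | 3 and 4 |

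The minimum count is 4 from 61 to 80 treated and becomes 5 at 81.

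**Chance of omission at 84 treated, no cases on placebo.** Let X be binomial with n = 56 and the true AR201 incidence. The pooled rule omits the event if X ≤ 4. A rule of 5% in either group needs 5% × 56 = 2.8, so 3 subjects, and omits the event if X ≤ 2.

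| True AR201 incidence | Pooled rule, P(X ≤ 4) | Per-group rule, P(X ≤ 2) | Difference, points |
|---|---|---|---|
| 6% | 76% | 34% | 42 |
| 7% | 65% | 24% | 41 |
| 8% | 53% | 16% | 37 |

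**Effect of the per-group rule on existing rows.** The pooled percentage is a weighted average of the two arm percentages. An event at 5% or more pooled is therefore at 5% or more in at least one arm, so the per-group rule adds rows and removes none.

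**The case against.** The strongest reply is that nothing here is false or contradictory. Tables of the most frequent events need some cut-off, and a pooled one selects rows without reference to arm and can be applied before unblinding. The per-group alternative has its own cost: it admits events seen in only 2 of 28 placebo subjects. This stands, and it is why the point is an improvement to a stated rule and not an error.

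Three stronger readings are tempting, and the documents do not support them.

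- **That product-specific events vanish from the safety report.** They do not. The incidence, severity and treatment-related summaries in Section 10.6 are unrestricted.
- **That the rule hides the events that best separate the arms.** The events left out have 3 or 4 cases on AR201 and none on placebo. If four cases fell at random, all would be on AR201 with probability (56 × 55 × 54 × 53)/(84 × 83 × 82 × 81) = 19%, and the two-sided Fisher p-value for 4/56 against 0/28 is about 0.30. A rate based on 4 events is also imprecise: exact Poisson 95% limits run from 1.1 to 10.2 events.
- **That the treatment-related table would consist mainly of AR201-only events.** Relatedness is judged by the investigator (Section 8.5), who is blinded (Section 3.3), so placebo events can be called related. Any placebo case lowers the AR201 count needed. The allergy symptoms expected to be common would clear either threshold.

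Nor do the documents show that exposure will differ between arms. In the one US placebo-controlled trial described in Section 1.1, withdrawals before maintenance were 5 of 40 on treatment (12.5%) and 2 of 15 on placebo (13.3%).

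**Conclusion.** The point holds as a minor one. As written, the 5% rule acts as roughly 7.5% to 9.3% for an event seen only on AR201, assuming 72 to 90 treated and 2:1 among those treated. A reader might take 8.9% as the fixed cut-off, but it belongs to exactly 84 treated; at 61 to 80 treated, an AR201-only event in 4 subjects is shown and only those in 3 are lost.

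The omission probabilities assume 56 treated on AR201 and no cases on placebo. The part attributable to pooling is the difference from the per-group rule, about 37 to 42 percentage points at true incidences of 6% to 8%, and not the full 53% to 76%. The consequence is confined to a few low-count rows in two supplementary tables; no trial conclusion changes.

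**What to change.** In both exposure-adjusted bullets of Section 10.6, define the most frequent events as those in at least 5% of subjects in either treatment group. At 56 and 28 treated this means 3 or more on AR201 (3/56 = 5.4%) or 2 or more on placebo (2/28 = 7.1%). Carry the same wording into the statistical analysis plan. If a per-group rule was already intended, the change only makes the text say so.

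The cost is a few more rows with small counts, including some events seen in as few as 2 placebo subjects. Data collection, trial conduct and all other analyses stay as they are.
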